1.0 BACKGROUND AND SIGNIFICANCE

1.1 Tooth Extraction Socket Preservation

Tooth extraction is often associated with resorption of alveolar ridge height and width and with compromised soft tissue contours¹⁻⁸. An increasingly common periodontal practice combines skilled surgical technique with extraction site grafting. These procedures are thought to retard resorption of the socket volume while lending some control over bone-fill – thereby preserving the integrity of the alveolar ridge for future reconstruction with dental implants.

Limited evidence-based data exists to support a variety of bone grafting materials used to prevent the resorption of bone in the extraction socket. Autografts, allografts, xenografts and alloplasts are all considered viable options to maintain and regenerate the site^{1-6, 8}.

Artzi et al.⁴ evaluated the histology and histomorphometric analyses of 15 extraction sockets in 15 patients treated with cancellous porous bovine bone mineral. All procedures involved extraction sockets of anterior teeth and premolars; primary closure of the extraction sockets was achieved with a pediculated split palatal flap. The bone fill of the extraction sockets was 82.3% lamellar type bone, located in the apical portion of the sockets, and the woven type of bone found in the coronal part of the sockets. The investigators concluded that the cancellous porous bovine bone mineral was present 9 months after the procedure and that resorbability of the bone graft material needed further assessment. In a second phase of the same study, Artzi et al.⁵, investigated the grafted extraction sockets by means of histochemical analysis and demonstrated the biocompatibility of the cancellous bovine bone mineral.

In another study, Froum et al.⁶ grafted 30 extraction sockets and divided them into three different groups. Bioactive glass and demineralized freeze-dried bone allograft (DFDBA) were used in the two test groups; the control group received no material at all. Flaps were coronally positioned to achieve closure of the site by primary intention. The bioactive glass group exhibited 59.5% of vital bone outperforming the DFDBA and non-grafted extraction socket groups that presented 34.7% vital bone formation 6 to 8 months following the surgical procedure. The difference in vital bone was not considered statistically significant among the three groups.

Data from these studies support the potential of different bone grafting materials to preserve the alveolar ridge after extraction. Concomitant investigations, however have reported that grafting materials may, in fact, impede natural post-extraction healing⁷. Thus the most efficacious intervention remains clouded by uncertainty.

1.2 Platelet Rich Plasma

The addition of platelet rich plasma (PRP) to graft materials is gaining clinical acceptance as an added stimulus to wound healing in both osseous and soft tissues. PRP, an autologous concentration of human platelets in a small volume of plasma, consists of growth factors derived from platelets degranulation and cell adhesion proteins such as fibronectin, vitronectin and fibrin. The mechanism of action is based on the activation of transmembrane receptors of adult mesenchymal stem cells, osteoblasts, fibroblasts, endothelial cells, and epidermal cell lines by the growth factors.

The results from twenty patients who underwent tooth extractions because of root fracture of periodontitis are reported by Anitua et al.⁹ One group received PRP; in five of the ten patients in this group PRP was mixed with autologous bone to prevent tissue collapse. The remaining ten patients were left untreated and served as controls. The epithelialization in all of the cases treated with PRP was complete and significantly better than in areas treated without PRP. Osseous regeneration of mature bone was greater in quantity and quality in the PRP sites. Some limitations of this study include the absence of statistical analysis and the utilization of bone grafts in five out of ten experimental PRP sites that might have contributed to the favorable results as well as the subjective evaluation of soft-tissue healing. More recent evidence to support supplementing bone grafts with PRP was published by Marx in 2004¹⁰.

Despite its clinical acceptance, the scientific evidence for the use of PRP is based on promising case series and case reports. There is little data available to indicate an evidence-based advantage of grafting plus PRP compared to grafting alone.

1.3 Recombinant Human Platelet Derived Growth Factors

Recently, a combination of purified recombinant human platelet derived growth factors (rhPDGF-BB) with a beta tricalcium phosphate bone substitute [β -tcp] has been approved to aid periodontal wound healing. PDGF stimulates the mitosis of alveolar and periodontal ligament cells and β -tcp acts as the delivery vehicle that releases the growth factors over time to promote periodontal regeneration¹¹.

As one of 11 centers, our group¹² studied PDGF versus a β -tcp control in a prospective, randomized, double-blind, controlled human clinical trial conducted in 180 subjects. All subjects exhibited existing periodontal defects and were treated with the same surgical method. The two different experimental groups included TCP with 0.3 mg/ml of rhPDGF-BB, TCP with 1.0mg/ml; TCP carrier alone served as the control. Radiographic evaluation was performed 6 months after the surgical procedure and involved measurement of the linear bone growth in mm. The two test groups presented superior linear growth reaching to 57% and 34% bone fill compared to the control bone fill of 18%. Soft tissue healing was better in the rhPDGF-BB groups and particularly the low dose rhPDGF-BB group. We concluded that “the efficacy observed in an infected and inflamed site may indicate the potential of this regenerative modality in other bony/soft tissue wound healing applications”.

1.4 Reconstruction with Dental Implants

Dental implants have been used in dentistry for decades in an attempt to reestablish function and aesthetics to areas of the mouth where natural dentition is lost^{13, 14}. Materials and designs of dental implants^{15, 16, 17} have evolved over the years to arrive at the optimal combination of materials, shape and surface texture that would induce permanence to the restoration.

1.5 Innovative Implant Design Features

Among the many innovations, implant surface topography has materialized as the focus of recent investigations, resulting in a body of evidence lending support to the premise that surface texturing influences osseointegration and has a positive affect on soft tissue adaptation to the implants.

Microtextured implant surfaces are thought to increase bone formation via the enhancement of osteogenesis, osteoconduction and osteoinduction processes¹⁸. Investigators, Buser et al¹⁹, in a mini-pig model, demonstrated that a modified titanium implant surface resulted in similar bone-to-implant

contact to hydroxyapatite surface and Wennerberg et al ^{20,21,22,23}, utilizing different particle size TiO₂ or Al₂O₃, enhanced the bone formation at the implant surface in the rabbit model.

Further investigations of implant surface characteristics by Hanson and Norton²⁴ showed the development of pits on the implant surface. These investigators described hemispheric pits of 1 to 5 µm in diameter and 1 to 5 µm in depth. The establishment of these pits is believed to increase the biomechanical interlock of implants with bone and make implant-bone interface more resistant to the forces of shear.

Other studies have shown that the modified implant surface topography alters the soft tissue- implant interface on the cellular level. The implant roughness inhibited the attachment and growth of epithelial cells while enhancing the growth of fibroblasts ^{25, 26, 27}. Implant microtextured surfaces increased bacterial colonization around implants without compromising the surrounding soft tissue health ²⁸.

Based on this evidence, innovative microtexturing of the implant surface appears to enhance tissue integration and to promote epithelial attachment to the implant.

1.6 Resorbable Blast Texturing

The bone response to resorbable blast textured (RBT) implant surfaces have been studied in New Zealand male rabbits²⁹. Twenty-four RBT implants were tested against a control group of twenty-four machined commercially pure titanium implants. All the implants were inserted into the femoral knee joint of the rabbits. The RBT implants were characterized by the plethora of osteoblastic cells residing in direct contact with the implant surface. Osteoid matrix was directly deposited on the RBT implant surface.

Another investigation by Novaes' group ³⁰ evaluated the bone-implant interface of four different types of implant surfaces, including machined titanium, plasma spraying, hydroxyapatite coating and resorbable blast texturing. The RBT implant surfaces exhibited a statistically significant more bone-implant contact over the machined titanium implant surfaces.

1.7 Laser MicroTextured Surface

The laser thread-textured implant surface (LTT) has been recently introduced to dentistry. Little evidence-based data is currently available; one report suggests that the LTT surface developed a stronger bond and demonstrated more resistance to tensile forces ³¹. Another study, utilizing a canine model, showed evidence that the laser modified surface was associated with extensive osseointegration via a high strength biomechanical interlock, less formation of fibrous tissue³².

1.8 A Rigorous Test

Innovative implant design features coupled with novel surgical technique are challenging prevailing concepts of therapy. The dual issues: adequate, healthy, osseous tissue and the design (surface texturing) of implant devices thus remain central to the long-term success of dental implant therapy.

In an effort to establish further clinical evidence the current study will assess and compare the efficacy of three randomly assigned different bone grafting applications, including a PRP enriched material, in non-adjacent aesthetic zone extraction sockets. Sites that have healed without augmentation will serve as controls.

The study will also assess and compare the efficacy of early reconstruction with two-stage dental implant restorations and evaluate the effects of an innovative implant collar surface topography on the longitudinal maintenance of peri-implant osseous and soft-tissue.

Early reconstruction with implants placed in newly formed regenerated bone may be more prone to crestal resorption regardless of implant design. Placing implants with differing surface topographies into augmented bone may therefore, represent the most rigorous test of potential bone-preserving implant design.

2.0 INVESTIGATIONAL DESIGN

2.1 Study Design

This prospective, randomized-controlled clinical trial will test three hypotheses. One, bone grafting is an efficacious method of enhancing the development of new bone fill in extraction sockets; two, adding growth factors to grafting materials will aid osseous healing and help to preserve aesthetically pleasing soft tissue contours; and three, surface topography at the collar of implants will influence longitudinal preservation of peri-implant bone at the alveolar crest.

2.2 Objectives of the Investigation

The overall objective of this investigation is two-fold:

1. To evaluate outcomes with respect to osseous and soft tissue healing of grafted and non-grafted extraction sockets.
2. To evaluate longitudinal stability of dental implants with differing surface topographies at the collar after placement into grafted extraction sockets and sockets that have healed naturally.

2.3 Hypotheses and Specific Aims

Hypothesis I

Bone grafted sites preserve alveolar ridge dimensions of extraction sockets more effectively than extraction sites that have healed without grafting.

Specific Aims

- 1: Compare alveolar ridge dimensions in grafted extraction sockets to that of sites healed without grafts after 8 weeks of post-extraction healing.

Hypothesis II

The addition of growth factors to bone grafting materials will enhance osseous and soft-tissue healing.

Specific Aims

- 2: Assess the efficacy of bone grafting with and without enrichment with growth factors to preserve the volume of bone in extraction sockets.

- 3: Compare soft tissue healing between groups at week-1, week-2, week-4 and after 8 weeks of post-extraction healing

- 4: Assess quantitative bone fill across groups after 2 months of post-extraction healing
- 5: Compare qualitative bone fill across groups after 2 months of post-extraction healing.
- 6: Assess and compare the relationship of osseous healing and implant stability at insertion across groups after 2 months of post-extraction healing.

Hypothesis III

Laser Thread Textured (LTT) dental implant will help preserve longitudinal peri-implant crestal bone more effectively than implants with Resorbable Blast Texturing (RBT).

Specific Aims

- 7: Assess the efficacy of LTT and RBT surface topographies when surgically implanted into extraction sockets.
- 8: Assess peri-implant soft-tissue healing adjacent to LTT and RBT surfaced implants.
- 9: Assess changes in longitudinal crestal bone level across extraction groups and between implant groups at 12 and 24 months after surgical implant placement.

3.0 STUDY POPULATION

3.1 Entrance Criteria

Eighty healthy adult patients (20 in each group) of any ethnicity or gender whose treatment plan includes extraction of maxillary anterior teeth and/or mandibular and/or maxillary pre-molars and their replacement with root-form dental implants will be consecutively recruited for enrollment in the study.

The study will include an initial minimum of six time-sensitive, clinic visits over eight consecutive weeks. Implants will be placed 8 weeks after extractions. Following implant placement, additional visits, necessary for health maintenance and implant restoration, will be scheduled at the study dentist's discretion. Participants will return for two follow-up visits at 12 and 24 months after implant placement.

Only treatment of non-adjacent sites will be included in the database. Each participant may have up to four non-adjacent sites selected for inclusion as study treatment sites.

Participants must be at least 19 years old with demonstrated ability to understand the proposed treatment recommendations and prognosis and be able to provide informed consent, in English, without the aid of ad-hoc translation from another language. Decisionally-impaired adults and/or minors, who cannot consent for themselves, will not be enrolled; women who are pregnant or lactating at the time of enrollment will be excluded. Women will be tested for current pregnancy status.

Prior to enrollment, prospective participants must agree to be available for the entire duration of the study, be compliant with needed study-related evaluations and demonstrate a willingness to comply with strict time-line requirements. Certain health and medication exclusions apply (table 1).

Table 1 Entrance Criteria

Inclusion	Exclusion
Existence of one or more non-adjacent teeth in the aesthetic zone that are scheduled for extraction	Pregnancy or nursing at the time of enrollment
Healthy enough to undergo the proposed therapy without compromise to their existing health status	Previous malignant neoplasm
Demonstrated willingness to comply fully with protocol time-line and procedural requirements	A known hypersensitivity to β -TCP or rhPDGF-BB
At least nineteen years old	A known hypersensitivity to Titanium metal
Able to read and understand written English without the aid of ad hoc interpretation	Any health condition that in the opinion of the clinical investigators may adversely affect bone healing
Able to cognitively understand the proposed study therapy and possible prognosis	Any medication that in the opinion of the clinical investigators may adversely affect bone healing
Able to consent for their own inclusion in the study	Any indication of an inability to make autonomous decisions

3.2 Visit Sequence

The study will include a minimum of six time-sensitive clinic visits over eight consecutive weeks. Implants will be placed 8 weeks after extractions. Following implant placement, additional visits, necessary for health maintenance and implant restoration, will be scheduled at the study dentist's discretion. Participants will return for two follow-up visits at 12 and 24 months after implant placement.

4.0 STUDY PROCEDURES

4.1 Enrollment and Treatment Planning

After completing an individualized, private consent discussion and obtaining informed consent, a pre-surgical assessment will be completed. Each enrolled participant will be seen for an initial evaluation to include assessments of medical and dental conditions that will verify compliance with entrance criteria and for collection of demographic data.

Participants will be assigned a unique identification number. Information will be recorded on baseline case report forms (CRFs) developed specifically for this study.

Through consultations with prosthodontic clinicians, the documented treatment plan will be reviewed and revised if necessary to develop a therapy that will be of most benefit to the participant.

4.2 Randomization

Participants will be stratified for smoking status and randomized to one of four extraction groups; three experimental groups utilizing three different bone grafting applications and a control group where extraction sockets will be allowed to heal naturally. A secondary randomization will be conducted to select one tooth site per subject to receive trephine sampling for histology evaluation. At the time of enrollment, each participant in groups 1-4 will be further randomized into one of two implant strata.

4.3 Randomized Extraction Groups

Group 1. Atraumatic extractions followed by saline irrigation and natural healing [CONTROL]

Group 2. Atraumatic extractions followed by Freeze-Dried Bone Allograft (FDBA)/Tri-Calcium Phosphate (TCP) + collaplug

Group 3. Atraumatic extractions followed by FDBA/TCP/Platelet-Rich Plasma (PRP) +collaplug

Group 4. Atraumatic extractions followed by FDBA/TCP/Platelet-Derived Growth Factors (PDGF) + collaplug

4.4 Randomized Implant Groups

Each subject will receive two-stage dental implants with the same overall design features with two different surface treatments at the implant collar. Subjects with multiple sites will receive the same implant design in all study sites.

Group-A: Laser Thread Texturing (LTT) collar surface topography

Group-B: Resorbable Blast Texturing (RBT) collar surface topography

4.5 Pre-surgical Procedures

Oral impressions will be made and if a temporary replacement for the teeth to be extracted is required, a temporary Essix retainer will be fabricated. The Essix retainer, a removable prosthesis, will protect the healing tissue in an aesthetically pleasing manner but will not impede the clinical observation of study sites. Study casts may also be used to fabricate a surgical guide prior to implant surgery.

4.6 Surgical Extractions

All surgeries will be performed by qualified clinicians in an appropriately equipped surgical operatory located in the Periodontal Clinic at UAB School of Dentistry.

Prior to extraction surgery, participants will be given a loading dose of antibiotics based on their medical history and concomitant medications. A suggested prophylactic regimen follows:

2 gm of Amoxicillin 1 hour prior to the procedure followed by 500mg (TID) for 7 days

Patients with reported allergy to Amoxicillin:

600mg Clindamycin 1 hour prior to the procedure followed by 300mg (TID) for 7 days

The facial area will be scrubbed and the oral cavity disinfected by rinsing for 1 minute with a (0.12% chlorhexidine gluconate) antimicrobial oral rinse. Prior to extractions clinical photographs will be taken from the buccal and occlusal aspects. Photographs will be taken in a 1:1 ratio using a Nikon D-70 camera with a sunpack ringflash.

After preparation and isolation of the surgical area, anesthesia will be achieved in the region by regional block or local infiltration. Conscious sedation may be added at the surgeon's discretion to help manage patient anxiety.

The teeth will be extracted as atraumatically as possible, without raising a flap, utilizing periotomes and the Easy Extrac system. Grafting procedures will include the use of FDBA and collagen plugs in all experimental groups. In all groups, the integrity of the remaining socket walls will be assessed and measurements recorded on the surgical CRF. The sockets will be debrided and a bleeding surface created by decorticating the socket walls with either a curette or a surgical round burr.

4.7 Grafting Extraction Sockets

After extractions, sockets will be grafted according to each participant's assigned randomization group.

Group-1: Each socket will be irrigated with sterile saline and allowed to heal naturally [control group].

Group-2: Each socket will be grafted with freeze dried bone allograft (FDBA) mixed with Tri-calcium phosphate (TCP) 8:2 ratio; reconstituted with sterile saline.

4.7-2a Irrigate sockets with sterile saline

4.7-2b Pack the graft into each of the study sites using mild pressure achieving complete fill of the sockets.

4.7-2c Trim a 3mm section of collaplug and secure it over the grafted areas with 4.0 Vicryl crossing mattress sutures.

Group 3: Each socket will be grafted with an 8:2 ratio FDBA/TCP graft reconstituted with Platelet Rich Plasma (PRP).

4.7-3a Collect 9-18cc blood sample from the patient via venipuncture prepare the PRP following the Cascade Fibrinet System (Appendix A)

4.7-3b Mix PRP in the FDBA.TCP graft.

4.7-3c Irrigate sockets with sterile saline.

4.7-3d Pack the graft into each of the study sites using mild pressure achieving complete fill of the sockets

4.7-3e Trim a 3mm section of collaplug and secured it over the grafted areas with 4.0 Vicryl crossing mattress sutures.

4.7-3f Once secured in place, the soak the collaplug with PRP.

Group 4: Each socket will be grafted with an 8:2 ratio FDBA/TCP graft reconstituted with recombinant platelet derived growth factor (PDGF).

4.7-4a Irrigate sockets with sterile saline.

4.7-4b Apply PDGF into the sockets completely wetting all socket walls.

4.7-4c Mix PDGF with GEM-21S (product insert Appendix B)

4.7-4d Pack the graft into each of the study sites using mild pressure achieving complete fill of the sockets

4.7-4e Trim a 3mm section of collaplug and secure it over the grafted areas with 4.0 Vicryl crossing mattress sutures.

4.7-4f Once secured in place, soak the collaplug with PDGF.

After completion of procedures the Essix retainer (if used) will be fitted and placed.

A CBCT scan will be made to include images of each study site. Prescriptions for anti-bacterial mouth wash, antibiotics, and pain relief will be provided based on individual patient needs. An ice-pack will be dispensed. Verbal and written home care instructions will be given and the patient will be scheduled for a follow-up appointment.

4.8 Surgical Extraction Data Collection

The following data points will be collected and recorded on the surgical CRF: A description of the integrity of each of the socket walls will be recorded as follows.

4.8-1 Measurements of the Mesio-distal distance and the buco-lingual distance of the socket walls

4.8-2 Measurements of dehiscence and fenestration defects made with a UNC-15 periodontal probe in relation to the adjacent socket crest and rounded up to the nearest millimeter.

4.8-3 Wound Measurements – Mesio-distal distance and bucco-lingual distance of the soft tissue wound margins after suturing made with a UNC-15 periodontal probe and rounded to the nearest millimeter.

4.9 Post-Extraction Evaluations

Participants will return to clinic for oral evaluations as close to 7-days after the extraction/grafting procedure as possible and again at 14 days; sutures will be removed at the 14-day visit. An additional follow-up visit will be scheduled approximately 1-month following extractions. Healing will be closely monitored and appropriate data recorded on follow-up CRFs.

At each visit, medical history will be reviewed and any changes documented. Information regarding adverse events will be captured and recorded following IRB and Federal reporting guidelines. Eight weeks after the extractions, each study subject will be appointed for a second CBCT scan, a bone-fill biopsy and surgical placement of implants.

Table 2 – Study Procedures Visits -1 — 8

Procedures	V- (-1) Screening	V-1 Pre-Tx	V-2 EXT/ G	V-3 Week 1	V-4 Week 2	V-5 Week 4	V-6 Week 8 implant s	V-7 Week 10	V-8 Expose Implant
Consent Discussion/Obtained	X								
Medical History Review		X	X	X	X	X	X	X	X
Tx Plan Review		X							
Impressions		X							
Essix Retainer		X							
Randomized to Tx Groups		X							
Biopsy site selection		X							
Pre-Surg Antibiotics			X				X		
Pre-Surg Oral Rinse			X				X		
Tooth Extraction			X						
Tx Group Procedure			X						
Venipuncture (group 3 only)			X						
Clinical Photographs			X	X	X	X	X		X
CBCT Scan			X				X		
Periapical Radiographs							X		X
Post-Surg Instructions/Prescriptions			X				X		X
Suture Removal				X					X
AE's recorded			X	X	X	X	X	X	X
Bone Biopsy							X		
Implant Placement							X		
Implant Exposure									X

Table 3 Study Procedures Visits 9 —12

Procedures	V-9 Impressions	V-10 Final Restoration	V-11 12 month	V-12 24 month
Medical History Review	X	X	X	X
Impressions	X			
Clinical Photographs	X	X	X	X
Final Restoration Attached		X		
Periapical Radiographs		X	X	X
AE's recorded	X	X	X	X
Soft-tissue assessments			X	X
Pocket Depth Measurements			X	X
Patient Satisfaction			X	X

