11.0 COSTS TO PARTICIPANTS

11.1 Procedure Fees

No fees will be charged to participants for the, teeth extraction, socket grafting materials, implant devices, implant surgery, CBCTT scans, radiographs, photographs, bone biopsy analysis, or clinical evaluations for the entire study.

Participants will be expected to pay a **\$1,000.00 restoration fee for each study site.** This one-time-only fee will cover costs related to laboratory and materials for the fabrication of the implant restoration prosthesis. This fee is to be billed to participants prior to the initiation of any surgical procedures.

Study visits are not designed to take the place of routine dental care. Over the course of the study participants will be expected to continue with regular dental check-ups with a dentist of their choice. Should the need arise patients who do not have a regular dentist of record will be referred in the appropriate manner for any non-study related dental treatment. Costs for non-study related treatment will be charged to the participant's account or to their insurance provider in the usual manner per dental school policy and will not be paid for from the study account

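### The graft arm is assigned one visit before extraction, and nothing in the supplied text conceals it from the surgeon who extracts and prepares the socket

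*Combined protocol and SAP*

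**What the plan says.** Table 2 places "Randomized to Tx Groups", "Tx Plan Review" and "Biopsy site selection" in the V-1 (pre-treatment) column. "Tooth Extraction" and the group procedure are in the V-2 column. The interval between the visits is not given.

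Section 4.2 gives no time for the graft randomization. It says that the implant randomization is done at enrollment, among participants who already belong to one of the four graft groups. The Synopsis (Procedures) says that the surgical work follows a randomization table. No sealed, central or otherwise concealed release is described.

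Section 4.6 asks for extraction with as little trauma as possible and for decortication with a curette or a round burr. It adds: "In all groups, the integrity of the remaining socket walls will be assessed and measurements recorded on the surgical CRF". Section 4.8 lists the socket and defect measurements. Section 4.7 then describes grafting by arm, and its Group 3 steps begin "Collect 9-18cc blood sample from the patient via venipuncture prepare the PRP following the Cascade Fibrinet System".

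Section 5.5 masks the laboratory technicians. No supplied section masks the surgeon or the person who measures the socket.

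**The concern.** Randomization protects the comparison only from the point at which nobody can act on the assignment. Here a full visit boundary, and then the whole of the extraction, lie between assignment and the first step that differs by arm. A surgeon who knows that a socket will be left empty may extract or decorticate it differently from one that will be grafted. A participant or site may also leave between V-1 and V-2 for reasons linked to the arm.

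The first route is the more serious. It changes the ridge itself before any image is taken, so masked reading of the scans would not remove it. The contrast most exposed is control against the three graft groups combined, which is the SA-1 test. The SA-2 comparison of bone volume is exposed in the same way.

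**Working it through.** **Order of events, from the documents**

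| Step | Where stated | When |
|---|---|---|
| Treatment plan review | 4.1; Table 2 | V-1, order relative to randomization not stated |
| Graft-arm randomization | Table 2 (no time in 4.2) | V-1 |
| Biopsy site selection | Table 2 | V-1 |
| Extraction, debridement, decortication | 4.6; Table 2 | V-2 |
| Socket and defect measurements | 4.6, 4.8 | V-2 |
| Group 3 venipuncture | 4.7; Table 2 | V-2; 4.7 lists it under grafting, after extraction |
| Grafting | 4.7 | V-2 |
| First CBCT | 4.7, 8.1 | V-2, after grafting |

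No step listed before the sockets are prepared and measured is described as differing by arm. The early assignment therefore serves no purpose that the text states, apart from the section 4.2 sentence that assumes a graft group at enrollment.

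**What reaches the analyses.** Section 12.4 tests SA-1 by a group contrast on ridge dimensions at 8 weeks, and SA-2 by comparing mean bone volume. Smoking is the only covariate named for all models. The V-2 probe readings are not inputs to either model. Bias would therefore enter through the physical state of the ridge or through who remains in each arm, not through those readings.

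**The plan's own power figure.** Inputs from section 12.5: effective sizes 25 and 75, difference 0.50 sd, two-sided 0.05. The noncentrality is 0.50 / √(1/25 + 1/75) = 0.50 / 0.2309 = 2.165 on 98 degrees of freedom. Power is 57.3% by the t-test (58.1% by the normal approximation), against 57% stated. The difference detectable with 80% power is 0.653 sd, against about 0.65 sd stated. Both reproduce, and changing the time of allocation alters neither.

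**Illustration on assumed losses.** The documents give no loss between V-1 and V-2. Suppose k of the 20 controls left, no one left the graft arms, and those who stayed differed from those who left by D = 0.5 or 1.0 sd. The effective control size is then 25 × (1 − k/20), and the control mean shifts by (k/20) × D. Type I error is by the normal approximation with SE = √(1/n₁ + 1/75), where n₁ is that effective control size.

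| k (assumed) | Effective controls | Power at 0.50 sd | Shift, D = 0.5 / 1.0 | Type I error, D = 0.5 / 1.0 |
|---|---|---|---|---|
| 1 | 23.75 | 55.7% | 0.025 / 0.05 sd | 5.1% / 5.5% |
| 2 | 22.5 | 54.0% | 0.05 / 0.10 sd | 5.5% / 7.0% |
| 4 | 20 | 50.3% | 0.10 / 0.20 sd | 6.8% / 12.5% |
| 5 | 18.75 | 48.3% | 0.125 / 0.25 sd | 7.7% / 16.2% |

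One or two losses would matter little. Several selective losses from one arm would matter. The effect of differential handling at extraction cannot be calculated from the documents.

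**The case against.** The strongest reply is that assigned does not mean known. No section says that the arm is disclosed at V-1 or to whom, and the Manual of Procedures (Appendix E), which is listed but not among the supplied text, may describe a concealed release. The Synopsis also calls the surgical procedures standardized, and section 4.6 describes one socket preparation for all groups. This stands as a limit on the claim: the gap is missing protection, not demonstrated disclosure.

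A reader might infer more than the documents support:

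- **That the treatment plan is still open after assignment.** Section 4.1 says "the documented treatment plan will be reviewed and revised if necessary", but the review is at the same visit as randomization, and sections 4.1 and 4.2 and the rows of Table 2 put it first. The sequence is not fixed, so this is not shown.
- **That the fee is still open.** Section 11.1 says "This fee is to be billed to participants prior to the initiation of any surgical procedures". Billing could come before or after randomization.
- **That biased probe readings carry into SA-1 or SA-2.** No stated model uses them. A possible 1 mm rounding shift is therefore not a measure of bias in those tests.
- **That 1/20 = 5% of an arm per lost participant shows the harm.** That arithmetic holds for a loss at any time and is no evidence of bias.
- **That the V-2 medical history is a second eligibility screen.** Tables 2 and 3 mark it at every visit from V-1 on.

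A practical objection also stands: moving allocation conflicts with the implant-randomization sentence in section 4.2 and affects when Group 3 material can be prepared. Both need handling in the amendment.

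**Conclusion.** The point holds in a limited form. The schedule assigns the graft arm a visit before extraction, and the supplied text does not keep it from those who extract, prepare and measure the socket. Differential handling, or selective loss between V-1 and V-2, could bias SA-1 and SA-2, and the first of these is beyond repair by masked reading.

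The size is unknown, because neither differential handling nor pre-treatment loss is quantified in the documents. The figures in the loss table rest wholly on assumed losses confined to the control arm and on an assumed difference between leavers and stayers. The conclusion also assumes that no concealment procedure exists in material outside the supplied text. This is a worthwhile low-cost improvement to a stated schedule, not evidence that the comparison is already compromised.

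**What to change.** 1. In section 4.2 and Table 2, record the list of study sites on the baseline CRF at V-1.
2. Move the graft-arm allocation to V-2, after the teeth are out, the sockets are prepared, and the 4.8-1 and 4.8-2 measurements are on the surgical CRF. If allocation must stay at V-1, hold it in a concealed source and disclose it only at that point. Participants lost before V-2 have then still been randomized and should be reported by arm.
3. State who releases the arm and to whom.
4. Amend the section 4.2 sentence on implant randomization at enrollment so that it no longer presupposes a known graft group.
5. Reconcile the timing of the Group 3 venipuncture and PRP preparation with this order. Section 4.7 lists them under grafting after extraction, and Table 2 gives only V-2. The clinical sequence is for the sponsor to settle.

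The cost is protocol wording and an edit to Table 2. Materials for all four arms must be on hand at V-2, and Group 3 preparation may lengthen that visit. Planned N, smoking strata, number of visits and power are unchanged. The change does not address the first CBCT being taken after grafting (section 8.1), which is a separate matter.
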